## 6 Overall statistical principles

All applicable statistical tests will be 2-sided and will be performed using a 5% significance level. Two-sided 95% confidence intervals (CIs) will be presented. All analyses are seeking to show a difference, rather than equivalence or non-inferiority.

In general terms, categorical data will be presented using counts and percentages, whilst continuous variables will be presented using the mean, standard deviation (SD), median, lower quartile, upper quartile, minimum, maximum, and number of patients with an observation (N). Data will be split by time point where applicable.

Where there is missing data for an outcome variable, in the first instance, those records will be removed from any formal statistical analysis relating to that outcome variable, unless otherwise specified. In tabulations, numbers of missing observations will be provided, but percentages will not include them.

The main statistical analyses for primary and secondary outcomes will be adjusted for the minimisation variables: age, sex, baseline plasma troponin concentration unless doing so causes problems due to collinearity. Baseline troponin will be log transformed. Age and log baseline troponin will be adjusted for as a linear term, unless there is strong evidence of a departure from linearity for groups of related analyses. A group of related analyses is, e.g., the relationship between age and troponin, for all troponin analyses. This decision will be taken without looking at the unblinded treatment data, and taking care not to over-interpret smaller p-values in larger datasets, which may reflect the number of patients in the analysis rather than the magnitude of the effect. If a linear model is not adequate, then a fractional polynomial with two terms will be used. In general, analyses will be presented in subgroups of patients based on the presence of coronary 18F-fluoride uptake, and so this will not be adjusted for unless otherwise specified. The precise details of the minimisation variables are in the DIAMOND randomisation description document. Results of unadjusted statistical analyses will also be presented, although baseline measurements of outcome variables will always be adjusted for.

Distributional assumptions underlying the statistical analyses will be assessed by visual inspection of residual plots. Normality will be examined by normal probability plots. If the distributional assumptions of the parametric approach are not satisfied, further data transformation (to alleviate substantial skewness (i.e. normalizing) or to stabilise the variance), or other suitable methods will be considered, taking into account the level of normality in similar analyses. If analyses do not follow this SAP for any reason, an updated SAP will be written together with the reasoning for the action taken. This will also be documented in the statistical report.

All analyses and data manipulations will be carried out using SAS [1].

## 7 List of analyses

*Note: Throughout this document, “study entry” is defined as the randomisation date.*

### 7.1 Recruitment and retention, and definition of analysis populations

No formal statistical testing will be performed. The date of first and last patient randomised, and the number of patients randomised will be reported.

A CONSORT flow chart will be provided by the statistics team. Reasons for non-inclusion in the study (prior to randomisation) will be categorised. The number of patients discontinued early from the study will be summarised by reason for withdrawal and treatment. The number of patients in each treatment group will be specified for per protocol, and safety populations, with sufficient detail to explain why patients are excluded from each population.

The following will be presented:

- Number and percentage of patients who were ineligible for inclusion in trial (if any – it should not have been possible to randomise such patients).
- Numbers of patients who were randomised but never treated.
- Numbers of patients who received the opposite treatment to that allocated (if there are any)

- A listing of patients where the blind was broken early will be presented, including details of allocation, timing and reason for breaking blind, and outcome.

## 7.2 Baseline Balance

No formal statistical testing will be performed. These will be produced for the per protocol population, and all patients randomised. The following will be presented and summarised by allocated treatment:

### Demographics and Minimisation variables

- Age, as categorised (<65,  $\geq$ 65) in the minimisation algorithm (this is also the cut-off required for the EUDRACT portal). Age will also be presented as a continuous variable.
- Sex
- BMI
- Baseline plasma troponin concentration as categorised in the minimisation algorithm. This will also be presented as a continuous variable.
- The presence of coronary 18F-fluoride uptake as categorised in the minimisation algorithm.

### Other baseline variables:

- Smoking Status
  - Current smoker
    - Average cigarettes smoking per day
  - Smoking history
    - Stopped smoking (<1/ $\geq$  1 year)
- Cardiac History
  - Stable angina
  - History of acute coronary syndrome
  - Days between randomisation and date of most recent ACS
  - Previous PCI
  - Days between randomisation and date of most recent PCI
  - Previous CABG
  - Days between randomisation and date of most recent CABG
  - History of cardiac failure
  - Hypertension
  - High cholesterol/on cholesterol lowering treatment
  - History of atrial fibrillation (paroxysmal or persistent)
  - Type 1 diabetes
  - Type 2 diabetes
  - Treatment for diabetes either Type 1 or Type 2
  - Peripheral vascular disease
  - Previous stroke or TIA
  - Rheumatoid arthritis
  - Family history of coronary heart disease/stroke
  - ASSIGN score
- Concomitant Medication
  - Statin

---

 See ASSIGN score betas.docx for details

- Beta-blocker
- ACE inhibitor/angiotensin receptor antagonist
- Physical Examination
  - Heart rate
  - Systolic blood pressure (mmHg)
  - Diastolic blood pressure (mmHg)
- Blood Results at baseline visit
  - Haemoglobin (g/L)
  - Urea (mmol/L)
  - Creatinine (umol/L)
  - WBC ( $\times 10^9$ /L)
  - Sodium (mmol/L)
  - eGFR (mL/min) – This will be reported as 31-60 / >60
  - Platelets ( $\times 10^9$ /L)
  - Potassium (mmol/L)
  - Total cholesterol (mmol/L)
  - LDL (mmol/L)
  - HDL (mmol/L)
  - Triglyceride (mmol/L)
  - Random glucose (mmol/L)
  - HbA1c (mmol/mol)
  - hsTnI (ng/L)

### 7.3 Compliance

The number of patients who received <80%, 80-90%, >90% of their study medication, using pill counts, and the following formula.

$$\text{Compliance (\%)} = \frac{\text{Pill Taken}}{\text{Days} \times 2} \times 100$$

Note: Compliance will be calculated based on pill counts at visits. Days will be calculated as days from previous visit date to current visit date. Expected pill taken at visits will be days x2. If participant forgot to bring her/his pill boxes at 30 days visit but bring those at 3 months visits, compliance at 3 months will be used for 30 days compliance.

Reasons for compliance less than 80% will be provided if available.

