6.5 PARTICIPANT COMPLIANCE AND ACCOUNTABILITY

Members of the research team will assess treatment compliance at attendance of each of the study visits by interview and pill count. Non-compliance with the dosing regime will only be considered a protocol deviation if the participant takes less than 90% of the planned dose. Any unused study medication will be returned to the Pharmacy Department at the Royal Infirmary for destruction.

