7.2 STUDY ASSESSMENTS

This is a prospective single-centre randomized double blind matched placebo controlled trial of ticagrelor 90 mg twice daily in patients with stable coronary artery disease for 1 year. Subjects will attend for clinical assessments at 30 days, 3, 6, 9 and 12 months with a final computed tomography coronary angiogram at the end of the study. The randomisation visit must be conducted within 25 days of the baseline visit.

	Screening -183 days	Baseline (-15 days ±10 days)	Randomisation (Day 0)	30 days (±5 days)	3 months (±14 days)	6 months (± 14 days)	9 months (± 14 days)	1 year (± 14 days*)
Eligibility Criteria and PIS	X							
Continuing eligibility confirmed			X	X	X	X	X	
Consent	X							
Concomitant medications		X		X	X	X	X	X
Clinical History		X		X	X	X	X	X
Physical Examination		X						
Clinical Biochemistry and haematology	X (if not checked in past 6 months)	X					X	
Blood sampling for hsTnI		X		X	X	X	X	X
Blood sampling for PMA		X		X				
12-lead ECG		X		X	X	X	X	X
AE/SAE Reporting		X		X	X	X	X	X
Treatment allocation/Medication dispensed			X		X	X	X	
Compliance check				X	X	X	X	X
18F-Fluoride PET		X	X		X	X		X
			Additional 18F-Fluoride PET scans will be performed in a subgroup only					
CT attenuation correction								
			CT attenuation correction is required prior to each PET scan for the subgroups who undergo this					
CT Calcium Score		X						X
CT Coronary Angiogram		X	Repeat CTCA scans will be performed at the time of each PET scan for those who are in the reproducibility and natural history sub-studies					X*

* Where it is not possible for the CT scan at the 1 year visit to be performed at the same time as the other 1 year study assessments participants may be asked to attend an additional visit during which the CT scan will be performed. In this situation the remainder of the study assessments will be performed within the planned visit window (± 14 days) and the CT scan will be arranged for the earliest practicable opportunity.

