## 5 Description of analysis datasets

The analysis datasets are detailed below. All analyses will be performed on the per protocol population unless otherwise specified.

**Per protocol** we will exclude any patient who does not have a blood sample for estimation of the plasma troponin concentration or whose compliance is deemed inadequate (as estimated from pill counts) at the 30 day visit. Inadequate compliance is defined as <80% using the formula in Section 7.3. Patients will be analysed according to treatment received.

**Safety** the Ticagrelor group will include all subjects who received any Ticagrelor study medication, regardless of the group they were originally allocated to. The placebo group will include all patients who received some study medication, but where all of this was placebo, regardless of the group they were originally allocated to. The group who were randomised but did not receive any medication at all will be reported separately.

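### Read literally, SAP 7.3 sets about 91 days of tablets against about 61 days when a 3-month count replaces a missed 30-day count, so steady adherence of about 54% meets the 80% cut

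*SAP*

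**What the plan says.** SAP 5 makes the per-protocol set the default: "All analyses will be performed on the per protocol population unless otherwise specified". It leaves out patients "whose compliance is deemed inadequate (as estimated from pill counts) at the 30 day visit", and sets the cut: "Inadequate compliance is defined as <80% using the formula in Section 7.3". SAP 7.4 names no other population, so this cut helps to decide who enters the primary analysis.

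The formula in SAP 7.3 is tablets taken, divided by twice the number of days, times 100. Two notes fix the denominator: "Days will be calculated as days from previous visit date to current visit date" and "Expected pill taken at visits will be days x2". For a patient who came to the 30-day visit without the boxes and brought them at 3 months, "compliance at 3 months will be used for 30 days compliance". No other meaning of Days is given for that case, and no start date is given for the tablets taken.

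Protocol 6.5 plans a check at every visit: "Members of the research team will assess treatment compliance at attendance of each of the study visits by interview and pill count". In the visit table of protocol 7.2, the row "Treatment allocation/Medication dispensed" is marked at randomisation, 3, 6 and 9 months, and not at 30 days. Protocol 6.3 gives two tablets a day.

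**The concern.** The formula works when boxes are counted at every visit. The 30-day count then covers randomisation to day 30, the 3-month count covers the time since the 30-day count, and in each case Days covers the same dates.

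It fails when the 30-day count is missed. Nothing new is dispensed at 30 days, so the boxes counted at 3 months are the ones issued at randomisation, and the tablets gone from them cover the whole period. The written denominator still starts at the 30-day visit. Numerator and denominator cover different dates, and the ratio is too high.

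What is at stake is membership of the primary analysis set. The SAP plans 55 patients per group with 18F-fluoride uptake. It defines only a per-protocol and a safety set, and gives no version of the primary model in another population. No planned analysis would show whether patients wrongly let in had changed the result.

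**Working it through.** The plan gives no figure of its own on this point, so there is nothing to reproduce.

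**Inputs**
- a, day of the 30-day visit: 30, window 25 to 35 (protocol 7.2).
- b, day of the 3-month visit: 91, window 77 to 105. The protocol gives 3 months ± 14 days but no day number, so day 91 is an assumption.
- Two tablets a day (protocol 6.3) and a cut of 80% (SAP 5).
- Boxes counted at 3 months were issued at randomisation (dispensing row, protocol 7.2). This is an inference from the protocol; the SAP does not say it.

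**Literal reading.** At steady adherence p, tablets taken are 2bp and expected tablets are 2(b − a). Computed compliance is therefore p × b/(b − a). The ranges put the two visits at opposite ends of their windows.

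| Quantity | Formula | Days 30 and 91 | Days 35 and 77 | Days 25 and 105 |
|---|---|---|---|---|
| Inflation factor | b/(b − a) | 91/61 = 1.49 | 77/42 = 1.83 | 105/80 = 1.31 |
| Steady adherence that scores 80% | 0.8(b − a)/b | 53.6% | 43.6% | 61.0% |
| Steady adherence that scores 100% | (b − a)/b | 67.0% | 54.5% | 76.2% |

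Taking 3 months as day 90 or day 92 changes the factor only to 90/60 = 1.50 or 92/62 = 1.48.

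In whole tablets at days 30 and 91, expected tablets are 2 × 61 = 122 as written and 2 × 91 = 182 over the full period. A patient who took 98 tablets scores 98/122 = 80.3% and is included, although 98/182 = 53.8%. With 97 tablets the score is 97/122 = 79.5% and the patient is excluded.

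A patient who took nothing to day a and every tablet afterwards scores (b − a)/(b − a) = 100% and is included in an analysis of troponin at day 30.

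**Matched denominator.** If Days runs from randomisation to the 3-month visit, steady adherence p scores p, and the break-even returns to 80% (146 of 182 tablets). Changing adherence is handled as follows.

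| Pattern | Formula | Days 30 and 91 | Days 35 and 77 | Days 25 and 105 |
|---|---|---|---|---|
| Nothing to day a, then full | (b − a)/b | 67.0% | 54.5% | 76.2% |
| Full to day a, then stopped | a/b | 33.0% | 45.5% | 23.8% |
| Lowest adherence to day a that reaches 80% if full afterwards | (0.8b − (b − a))/a | 39.3% | 56.0% | 16.0% |

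The first patient is now correctly excluded. The second, fully adherent up to the 30-day sample, is wrongly excluded. The third is wrongly included. The cause is that 61/91 = 67% of the substituted interval falls after the 30-day sample. Matching the denominator removes the arithmetic error but not this one.

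**The case against.** The strongest reply is that no SAP sentence says 91 days of tablets are to be divided by 61 days. The interval for tablets taken is undefined, and the 91 days come from the protocol's dispensing row. The authors evidently knew that the same boxes could come back at 3 months, and a sensible analyst might take the previous visit to mean the last one with a count or dispensing. This stands in part: the 54% figure depends on the literal denominator and an inferred numerator. But the rule fixes Days without exception, and followed as written it misclassifies patients. SAP 8 has a second statistician program the primary outcome separately; two programmers could reasonably choose different Days and build different populations.

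Second, the literal result would give itself away. Full adherence would score 149%, and steady adherence above about 67% would exceed 100%. That may prompt a correction. However, steady adherence from about 54% to 67% passes without exceeding 100%, the SAP has no cap or check, and it does not say what Days should then become.

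Third, the group is narrow. At steady adherence, only patients between about 54% and 80% change class, and the literal error only adds randomised patients to the set. This stands, and limits the weight of the point.

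A reader might infer that the primary comparison is biased, perhaps in a known direction. The documents do not support that. They do not say how many patients forgot their boxes, how these divide between arms, or how their troponin values differ.

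**Conclusion.** The point holds as a defect in the written rule. For patients who forgot their boxes at 30 days and brought them at 3 months, the literal formula inflates compliance 1.49-fold (1.31 to 1.83). Steady adherence of about 54% (44% to 61%) then meets the 80% cut. This rests on three things: Days as written, boxes issued at randomisation and not counted until 3 months, and 3 months taken as day 91.

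It would be too much to say that 54% adherence will in fact be accepted, since an analyst may use the dispensing date. It would also be wrong to extend the fault to compliance values where the 30-day count exists; those are computed correctly. The number of patients affected, and the size and direction of any bias, are not derivable. The change should still be made, because the rule decides entry to the primary analysis and the repair needs no new data.

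**What to change.** In SAP 7.3, state that when the 3-month count stands in for a missed 30-day count, Days runs from the randomisation (dispensing) date to the 3-month visit. As the general rule, Days runs from the date on which the counted boxes were dispensed, or from the last visit at which those same boxes were counted, if later. Tying the rule to the boxes matters: with dispensing at 3 and 6 months, a rule based simply on the last dispensing could recreate the mismatch at 9 months if the 3-month boxes were first counted then.

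Flag patients classified by substitution and report their number by arm. Run the primary model once including all flagged patients who have a 30-day troponin and once excluding all of them, because about two-thirds of the substituted interval follows the sample.

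The cost is a short change of wording, one flag variable and two extra model runs. The 80% threshold and the use of pill counts are unchanged. The remaining drawback is that patients whose adherence changed around day 30 can still be misclassified in the main analysis; the two extra runs show whether that matters to the result.

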### 7.4 Primary outcome: Plasma high sensitivity cardiac troponin I (hsTnI) concentration at 30 days in patients with coronary 18F-fluoride uptake

As Troponin I at 30 days is skewed, it will be log transformed prior to analysis. A value of 0.5ng/l will be used for values below the limit of detection. When reporting summary statistics and results of analyses, the logged and unlogged results will be reported, i.e. if we report a mean of the logged values, we will back-transform this mean to the original unlogged scale for ease of interpretation.

Troponin I at 30 days, in patients with coronary 18F-fluoride uptake at baseline, will be modelled in a linear regression model, adjusting for age, sex, and log baseline troponin I. Unadjusted analyses (still adjusted for log baseline troponin) will also be presented. The difference in means between the treatment groups will be presented, along with a 95% confidence interval and p-value. Descriptive statistics will be presented for baseline, 30 days and the change between baseline and 30 days. Numbers with missing data

values at baseline and 30 days will be reported, and descriptive statistics will be presented for the group with no missing data at either time point.

## 7.5 Secondary outcomes

### 7.5.1 *Plasma hsTnI concentrations at 30 days in patients without coronary 18F-fluoride uptake.*

As Troponin I at 30 days is skewed, it will be log transformed prior to analysis. A value of 0.5ng/l will be used for values below the limit of detection. When reporting summary statistics and results of analyses, the logged and unlogged results will be reported, i.e. if we report a mean of the logged values, we will back-transform this mean to the original unlogged scale for ease of interpretation.

Troponin I at 30 days, in patients without coronary 18F-fluoride uptake, will be modelled in a linear regression model, adjusted for age, sex, and log baseline troponin I. Unadjusted analyses (still adjusted for log baseline troponin) will also be presented. The difference in means between the treatment groups will be presented, along with a 95% confidence interval and p-value. Descriptive statistics will be presented for baseline, 30 days and the change between baseline and 30 days. Numbers with missing data values at baseline and 30 days will be reported, and descriptive statistics will be presented for the group with no missing data at either time point.

### 7.5.2 *High sensitivity cardiac troponin I (hsTnI) concentration at 30 days in total study population.*

As Troponin I at 30 days is skewed, it will be log transformed prior to analysis. A value of 0.5ng/l will be used for values below the limit of detection. When reporting summary statistics and results of analyses, the logged and unlogged results will be reported, i.e. if we report a mean of the logged values, we will back-transform this mean to the original unlogged scale for ease of interpretation.

Troponin I, in all patients, will be modelled in a linear regression model, adjusting for age, sex, and log baseline troponin I. Unadjusted analyses (still adjusted for log baseline troponin) will also be presented. The difference in means between the treatment groups will be presented, along with a 95% confidence interval and p-value. Descriptive statistics will be presented for baseline, 30 days and the change between baseline and 30 days. Numbers with missing data values at baseline and 30 days will be reported, and descriptive statistics will be presented for the group with no missing data at either time point.

A term for coronary 18F-fluoride uptake (Y/N) will be added into the model for all patients, and the p-value for the interaction between coronary 18F-fluoride uptake and the treatment effect will be presented.

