5.6 RANDOMISATION

5.6.1 Randomisation Procedures

Eligible patients will be randomized using a web-based randomization service to ensure allocation concealment. Given the modest sample size, we will minimise treatment allocation according to age, sex, baseline plasma troponin concentration and the presence of coronary 18F-fluoride uptake.

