9.2.2 Methods of Statistical Analysis

For the primary analysis, the change in plasma high-sensitivity troponin concentration from baseline to 30 days will be compared between the two treatment groups (ticagrelor and placebo) using linear regression, adjusting for the minimisation variables, in patients with coronary ¹⁸F-fluoride uptake. Prior to analysis, tests for normality will be undertaken and, where data are skewed, logarithmic transformation will be considered prior to analysis. Effect sizes and 95% confidence intervals will be calculated. Similar analyses will be performed for the assessment of troponin at 30 days in patients without coronary ¹⁸F-fluoride uptake, and in the study population as a whole; for troponin at 1 year; and for calcium score and plaque volume at 1 year at the site of baseline coronary ¹⁸F-fluoride uptake.

Statistical analysis will be performed using SAS. A two-sided $P<0.05$ will be taken as statistically significant. A full statistical analysis plan will be documented prior to data base lock. This will be overseen by the trial statistician in the Edinburgh Clinical Trials Unit.

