## 3 Introduction

This document details the criteria to be used for the definition of the analysis populations and the statistical methodology for analysis for the DIAMOND trial, a randomised trial of Ticagrelor to reduce markers of myocardial injury in patients with stable coronary heart disease and high-risk coronary atheroma. This document has been compiled according to the Edinburgh Clinical Trials Unit (ECTU) standard operating procedure (SOP) "Statistical Analysis Plans" and has been written based on information contained in the study protocol version 5.0, dated 31 January 2017.

DIAMOND is a single centre, randomised, parallel-group, double blind, placebo-controlled trial. Randomisation is at the individual level with a 1:1 allocation ratio, and is minimised on age, gender, baseline plasma troponin concentration, presence of coronary 18F-fluoride uptake (as detailed in the Randomisation System Description document). Patients are randomised to either Ticagrelor or matched placebo tablets. The aim is to recruit 220 patients, with a view to having 55 per group in the group with increased coronary 18F uptake.

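### The all-patient troponin models report the treatment effect without adjusting for 18F-fluoride uptake, a minimisation factor, and the treatment-by-uptake contrast is specified only as a p-value

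*SAP*

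**What the plan says.** Protocol 5.6.1 says the trial will "minimise treatment allocation according to age, sex, baseline plasma troponin concentration and the presence of coronary 18F-fluoride uptake", and SAP section 3 names the same four factors. Protocol 9.2.2 describes the primary analysis as "using linear regression, adjusting for the minimisation variables". It then asks for similar analyses in patients without uptake and in the whole study population, with effect sizes and 95% confidence intervals.

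SAP section 6 lists three adjustment variables: age, sex and baseline troponin. On uptake it explains that analyses are in general presented by uptake subgroup, "so this will not be adjusted for unless otherwise specified".

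For 30-day troponin in everyone, SAP 7.5.2 states: "Troponin I, in all patients, will be modelled in a linear regression model, adjusting for age, sex, and log baseline troponin I". The treatment difference, its 95% confidence interval and the p-value are attached to that model. A closing paragraph adds an uptake term to the all-patient model, and the output named for that step is that "the p-value for the interaction between coronary 18F-fluoride uptake and the treatment effect will be presented". SAP 7.5.3 follows the same two steps for the area under the troponin curve from 30 days to 1 year.

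Within-group treatment differences with 95% confidence intervals are planned in uptake-positive patients (7.4), in uptake-negative patients (7.5.1), and in both groups for the area under the curve (7.5.3).

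**The concern.** Within an uptake group, uptake is constant and there is nothing to adjust for. In the all-patient models it varies, so the reason given in SAP section 6 no longer holds. Yet the effect and interval reported there come from a model that leaves out a factor used to allocate treatment. When minimisation has balanced a prognostic factor, omitting it from the model puts its between-group variance into the residual. The model-based standard error is then larger than the true sampling variability.

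The second part concerns the contrast between uptake groups. Protocol 1.3 anticipates benefit only in patients with high-risk plaque, and section 3.1 asks whether an effect is particular to them. The interaction is the formal comparison behind that question. A non-significant p-value on its own does not tell a reader whether the two effects are similar or the data are too few to separate them. An interval does.

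**Working it through.** **Plan's own figures.** Protocol 9.1 gives 48 per arm. An unequal-variance t-test for 7.89 versus 3.95 ng/L with SDs 9.34 and 1.89 has 80.2% power at 48, so the figure is reproduced. The total is 110/0.60 = 183.3, against 183 stated. The calculations below use 110 uptake-positive and 73 uptake-negative patients. The documents give no figure for the all-patient model or for the interaction.

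**Log-scale inputs.** Protocol 9.1 gives troponin of 7.89 (SD 9.34) with uptake and 3.10 (SD 1.89) without. Assuming log-normality:
- Positive: log variance = ln(1 + (9.34/7.89)²) = 0.876 (SD 0.94); log mean = ln 7.89 − 0.438 = 1.628.
- Negative: log variance = ln(1 + (1.89/3.10)²) = 0.316 (SD 0.56); log mean = ln 3.10 − 0.158 = 0.973.
- Uptake difference D = 1.628 − 0.973 = 0.654.
- Pooled within-group variance W = 0.6 × 0.876 + 0.4 × 0.316 = 0.652.
- Share of log-troponin variance due to uptake: R² = 0.24D²/(0.24D² + W) = 0.1027/0.7547 = 0.136.

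**Standard error with uptake omitted.** Let r be the within-group correlation of log troponin between baseline and 30 days. It is not in the documents, so it is shown over a range. The same uptake difference is assumed at both times. After baseline adjustment the remaining uptake effect is D(1 − r), so

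SE ratio = √[1 + D²(1 − r)² × 0.24 × (1 − R²) / (W(1 − r²))].

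At r = 0.5: √[1 + 0.0222/0.489] = 1.022.

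| r | SE excess, formula | SE excess, simulation |
|---|---|---|
| 0.3 | 3.6% | 3.5% |
| 0.5 | 2.2% | 2.2% |
| 0.8 | 0.75% | 0.7% |

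A simulation of minimised allocation (183 patients, 6,000 runs per setting) gave type I error without uptake of 4.2% at r = 0.5, 4.6% at 0.7 and 5.1% at 0.85. With uptake it was 4.7% to 5.1%. The effect estimate is unbiased either way.

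**Interaction.** With a common residual variance, SE = √[4W(1 − r²)(1/110 + 1/73)]. At r = 0.8: √[4 × 0.2347 × 0.02279] = 0.146. The 95% interval on the ratio of treatment effects is then the estimate multiplied and divided by exp(1.96 × 0.146) = 1.33. The factor is 1.51 at r = 0.5 and 1.58 at r = 0.3. The interaction SE is √(1 + 110/73) = 1.58 times that of the uptake-positive effect.

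Power, taken as Φ(|ln ratio|/SE − 1.96), for an effect in uptake-positive patients and none in the others:

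| Reduction in geometric mean | r = 0.3 | r = 0.5 | r = 0.8 |
|---|---|---|---|
| 50% | 85% | 91% | 99.7% |
| 30% | 34% | 39% | 68% |
| 20% | 16% | 18% | 33% |

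Simulation with the unequal group SDs gives 86% to 99.8% for the 50% row and 13% to 30% for the 20% row.

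The 20% row is an assumption with no source in the documents. The 30% row has a link to the plan. If the planning SD of 1.89 on ticagrelor is taken literally, the log mean there is ln 3.95 − ½ ln(1 + (1.89/3.95)²) = 1.271. The geometric-mean ratio is then exp(1.271 − 1.628) = 0.70. That row keeps the larger variance in both arms, so it is only a guide.

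**The case against.** **The trial's main question does have estimates.** A reader might infer from the bare p-value that the stratified question gets no estimate. The documents do not support that. Effects with 95% confidence intervals are planned in each uptake group, and the primary analysis is one of them. The groups do not overlap, so for the 30-day log outcome a reader could subtract the two estimates and add their variances. What stands against this is that the contrast itself has no prespecified estimate or interval.

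**Uptake is added to the model.** The closing paragraphs of 7.5.2 and 7.5.3 could be read as the exception that section 6 allows. But the reported difference and interval belong to the model described before that step, and only the interaction p-value belongs to the step itself. At best it is unclear which model supplies the all-patient effect.

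**The protocol asks only for similar analyses.** Its covariate wording describes the primary analysis, where uptake is constant. That is fair, so the conflict is not absolute. The natural reading still carries the adjustment rule into the whole population, and the SAP's explanation does not cover that case.

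**A confidence interval is not ruled out.** SAP section 6 says generally that 95% intervals will be presented. Naming the p-value alone in 7.5.2 and 7.5.3 leaves this open.

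**The effect is negligible and safe.** This is largely right. It touches secondary analyses only, and the intervals are slightly too wide, not too narrow. It would also be wrong to call the interaction test weak without qualification, because at a 50% reduction it is well powered.

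**Conclusion.** The point holds as a free improvement. The all-patient effects in SAP 7.5.2 and 7.5.3 are specified from a model without a minimisation factor, for a reason that does not fit those models. For log 30-day troponin the cost is an interval about 0.7% to 2% too wide at correlations of 0.8 to 0.5, and 3.5% at 0.3. The direction is conservative, there is no bias, and the primary analysis is unaffected. No size is given for the 1-year area under the curve: the SAP names no log transformation for it, and it was not computed.

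The treatment-by-uptake contrast is specified as a p-value only. How much this matters depends on the true effect. At a 50% reduction the test will usually detect the difference. At an assumed 20% it usually will not, and a reader would then need the interval. Adding the interval does not raise that power; it shows how much remains uncertain.

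These sizes rest on log-normal troponin, the pilot means and SDs in the protocol, 60% uptake, and a correlation that the documents do not give.

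**What to change.** In SAP 7.5.2 and 7.5.3, state that the main all-patient model adjusts for age, sex, log baseline troponin and coronary 18F-fluoride uptake, and that the reported treatment difference, confidence interval and p-value come from that model. In SAP section 6, limit the sentence on not adjusting for uptake to analyses within uptake groups.

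Fit the interaction as a further step. Report it as a ratio of treatment effects with its 95% confidence interval beside the p-value, or as a difference if the area under the curve is analysed unlogged.

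The cost is one covariate, one line of output and two short edits. No further data or patients are needed.
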